	No Change	330 (96%)	359 (98%)
	Improvement	11 (3%)	4 (1%)
Left eye	n	342	364
	Worsening	1 (<1%)	2 (<1%)
	No Change	330 (96%)	359 (98%)
	Improvement	11 (3%)	4 (1%)
Subject (Worse eye)	n	342	364
	Worsening	1 (<1%)	2 (<1%)
	No Change	330 (96%)	359 (98%)
	Improvement	11 (3%)	4 (1%)

n is the number of eyes or subjects (worse eye) with exam findings at EOT visit worse than baseline, which will be used as denominator to calculate the percentage.

Example SAFE_T16
 Protocol: 205678
 Population: Safety

Table x.xxxx

Summary of Worst Grade of Corneal Events (GSK Scale) during Cycle 1-4 by Randomized Topical Corticosteroids Treatment

Timepoint		Treatment Group A (N = xx)		Treatment Group B (N = xx)	
		Eyes randomized to corticosteroids	Eye randomized to no corticosteroids	Eyes randomized to corticosteroids	Eyes not randomized to corticosteroids
Baseline	n	100	100	100	100
	Grade 0	70 (70%)	70 (70%)	70 (70%)	70 (70%)
	Grade 1	20 (20%)	20 (20%)	20 (20%)	20 (20%)
	Grade 2	10 (10%)	10 (10%)	10 (10%)	10 (10%)
	Grade 3	0	0	0	0
	Grade 4	0	0	0	0
Worst during Cycle 1-4	n	100	100	100	100
	Grade 0	70 (70%)	70 (70%)	70 (70%)	70 (70%)
	Grade 1	20 (20%)	20 (20%)	20 (20%)	20 (20%)
	Grade 2	10 (10%)	10 (10%)	10 (10%)	10 (10%)
	Grade 3	0	0	0	0
	Grade 4	0	0	0	0

Example SAFE_T17
 Protocol: 205678
 Population: Safety

Table x.xxxx
 Summary of Best Corrected Visual Acuity(BCVA) score (logMAR score) during Cycle 1-4 by Randomized Topical
 Corticosteroids Treatment

Timepoint	BCVA Score	Treatment Group A (N =xx)		Treatment Group B (N =xx)	
		Eyes	Eye not to	Eyes Randomized to	Eyes not to
Baseline	N	xxx	xxx	xxx	xxx
	Mean	x.x	x.x	x.x	x.x
	SD	x.xx	x.xx	x.xx	x.xx
	Median	x.x	x.x	x.x	x.x
	Min	x	x	x	x
	Max	xxx	xxx	xxx	xxx
Worst during Cycle 1-4	n	xxx	xxx	xxx	xxx
	Mean	x.x	x.x	x.x	x.x
	SD	x.xx	x.xx	x.xx	x.xx
	Median	x.x	x.x	x.x	x.x
	Min	x	x	x	x
	Max	xxx	xxx	xxx	xxx
	n	xxx	xxx	xxx	xxx
Worst change from baseline during Cycle 1-	No change/improve	xx(x.x%)	xx(x.x%)	xx(x.x%)	xx(x.x%)
	Possible worsened	xx(x.x%)	xx(x.x%)	xx(x.x%)	xx(x.x%)
	Definite worsened	xx(x.x%)	xx(x.x%)	xx(x.x%)	xx(x.x%)
Most frequent change from baseline during cycle 1-4	No change/improve	xx(x.x%)	xx(x.x%)	xx(x.x%)	xx(x.x%)
	Possible worsened	xx(x.x%)	xx(x.x%)	xx(x.x%)	xx(x.x%)
	Definite worsened	xx(x.x%)	xx(x.x%)	xx(x.x%)	xx(x.x%)
Worst during Cycle 1-4	BCVA decline to light perception	xx(x.x%)	xx(x.x%)	xx(x.x%)	xx(x.x%)
	BCVA decline to no light perception	xx(x.x%)	xx(x.x%)	xx(x.x%)	xx(x.x%)

Note: No change/improved vision is defined as a change from baseline <0.12; a possible worsened vision is defined as a change from baseline >=0.12 to <0.3; a definite worsened vision is defined as a change from baseline >=0.3 logMAR score.

Example SAFE_T18
 Protocol: 205678
 Population: Safety

Page 1 of 1
 (Data as of: 24APR2018)

Table x.xxxx

Summary of Onset Time to First Drug-Related Corneal Event (GSK Scale) by Randomized Topical Corticosteroids Treatment

	Treatment Group A (N=xx)		Treatment Group B (N=xx)	
	Eyes randomized to corticosteroids	Eyes randomized to no corticosteroids	Eyes randomized to corticosteroids	Eyes randomized to no corticosteroids
Number (%) of eyes experienced drug-related corneal event (GSK scale)	5 (50%)	4 (40%)	4 (40%)	5 (50%)
Time to initiation, days				
n	5	5	5	5
1-21	1 (20%)	1 (20%)	1 (20%)	1 (20%)
22-42	2 (40%)	2 (40%)	2 (40%)	2 (40%)
43-63	1 (20%)	1 (20%)	1 (20%)	1 (20%)
> 63	1 (20%)	1 (20%)	1 (20%)	1 (20%)
Mean	20.5	15.1	15.1	20.5
SD	1.44	1.24	1.24	1.44
Median	18	14	14	18
Min.	3	1	1	3
Max.	40	30	30	40

Example SAFE_T19
 Protocol: 205678
 Population: Ocular Sub-Study

Page 1 of 1
 (Data as of: 24APR2018)

Table x.xxxx

Summary of Onset Time to Initiation of Topical Corticosteroids Treatment in Eyes Not Randomized to Topical Corticosteroids Treatment

	Treatment Group A (N = xx)	Treatment Group B (N = xx)
Number (%) of eyes that initiated topical Corticosteroids Treatment	5 (50%)	4 (40%)
Time to initiation, days		
n	5	5
1-21	1 (20%)	1 (20%)
22-42	2 (40%)	2 (40%)
43-63	1 (20%)	1 (20%)
> 63	1 (20%)	1 (20%)
Mean	20.5	15.1
SD	1.44	1.24
Median	18	14
Min.	3	1
Max.	40	30

Note:

1: N reflects the number of eyes randomized to no topical corticosteroids treatment for ocular sub-study.

Example SAFE_T20
 Protocol: 205678
 Population: Safety

Page 1 of 1
 (Data as of: 24APR2018)

Table x.xxxx
 Shift in Corneal Events (per Ocular Exam) from Baseline to Worst During Cycle 1-4 by Randomized Topical
 Corticosteroids Treatment

Exam	Shift from Baseline to Worst (Cycle 1-4)	Treatment Group A (N = xx)		Treatment Group B (N= xx)	
		Eyes randomized to corticosteroids	Eyes not randomized to corticosteroids	Eyes randomized to Corticosteroids	Eyes not randomized to corticosteroids
Corneal Epithelium	n	100	100	100	100
	Normal to Normal	30 (30%)	30 (30%)	30 (30%)	30 (30%)
	Normal to Abnormal	50 (50%)	50 (50%)	50 (50%)	50 (50%)
	Abnormal to Normal	0	0	0	0
	Abnormal to Abnormal	20 (20%)	20 (20%)	20 (20%)	20 (20%)
Punctate Keratopathy	n	100	100	100	100
	None/Mild to None/Mild	30 (30%)	30 (30%)	30 (30%)	30 (30%)
	None/Mild to Moderate/Severe	50 (50%)	50 (50%)	50 (50%)	50 (50%)
	Moderate/Severe to None/Mild	0	0	0	0
	Moderate/Severe to Moderate/Severe	20 (20%)	20 (20%)	20 (20%)	20 (20%)
Corneal Ulcer	n	100	100	100	100
	Normal to Normal	30 (30%)	30 (30%)	30 (30%)	30 (30%)
	Normal to Abnormal	50 (50%)	50 (50%)	50 (50%)	50 (50%)
	Abnormal to Normal	0	0	0	0
	Abnormal to Abnormal	20 (20%)	20 (20%)	20 (20%)	20 (20%)
Microcystic Edema	n	100	100	100	100
	No to No	30 (30%)	30 (30%)	30 (30%)	30 (30%)
	No to Yes	50 (50%)	50 (50%)	50 (50%)	50 (50%)
	Yes to No	0	0	0	0
	Yes to Yes	20 (20%)	20 (20%)	20 (20%)	20 (20%)

CONFIDENTIAL

205678

Microcystic Without Edema	n	100	100	100	100
	No to No	30 (30%)	30 (30%)	30 (30%)	30 (30%)
	No to Yes	50 (50%)	50 (50%)	50 (50%)	50 (50%)
	Yes to No	0	0	0	0
	Yes to Yes	20 (20%)	20 (20%)	20 (20%)	20 (20%)
Subepithelial Haze	n	100	100	100	100
	No to No	30 (30%)	30 (30%)	30 (30%)	30 (30%)
	No to Yes	50 (50%)	50 (50%)	50 (50%)	50 (50%)
	Yes to No	0	0	0	0
	Yes to Yes	20 (20%)	20 (20%)	20 (20%)	20 (20%)
Corneal Neovascularization	n	100	100	100	100
	No to No	30 (30%)	30 (30%)	30 (30%)	30 (30%)
	No to Yes	50 (50%)	50 (50%)	50 (50%)	50 (50%)
	Yes to No	0	0	0	0
	Yes to Yes	20 (20%)	20 (20%)	20 (20%)	20 (20%)
Stroma	n	100	100	100	100
	Normal to Normal	30 (30%)	30 (30%)	30 (30%)	30 (30%)
	Normal to Abnormal	50 (50%)	50 (50%)	50 (50%)	50 (50%)
	Abnormal to Normal	0	0	0	0
	Abnormal to Abnormal	20 (20%)	20 (20%)	20 (20%)	20 (20%)
Active Opacity	n	100	100	100	100
	No to No	30 (30%)	30 (30%)	30 (30%)	30 (30%)
	No to Yes	50 (50%)	50 (50%)	50 (50%)	50 (50%)
	Yes to No	0	0	0	0
	Yes to Yes	20 (20%)	20 (20%)	20 (20%)	20 (20%)
Active Edema	n	100	100	100	100
	No to No	30 (30%)	30 (30%)	30 (30%)	30 (30%)
	No to Yes	50 (50%)	50 (50%)	50 (50%)	50 (50%)
	Yes to No	0	0	0	0
	Yes to Yes	20 (20%)	20 (20%)	20 (20%)	20 (20%)

Example SAFE_T21
 Protocol: 205678
 Population: Full Safety

Table x.xxxx
 Summary of Blurred Vision (CTCAE) Characteristics II

	2.5 mg/kg (N= xx)	3.4 mg/kg (N= xx)	3.4 mg/kg (N= xx)
Time to onset of first occurrence, days			
n	XX	XX	XX
Mean	XX.X	XX.X	XX.X
SD	XX.XX	XX.XX	XX.XX
Median	XX.X	XX.X	XX.X
Min.	XX	XX	XX
Max.	XX	XX	XX
1 - 21	XX (XX.X%)	XX (XX.X%)	XX (XX.X%)
22 - 42	XX (XX.X%)	XX (XX.X%)	XX (XX.X%)
43 - 63	XX (XX.X%)	XX (XX.X%)	XX (XX.X%)
64 - 105	XX (XX.X%)	XX (XX.X%)	XX (XX.X%)
>105	XX (XX.X%)	XX (XX.X%)	XX (XX.X%)
Outcome of first occurrence [1] (n=xx)			
Resolved	XX (XX.X%)	XX (XX.X%)	XX (XX.X%)
re-started with dose delay and reduction	XX (XX.X%)	XX (XX.X%)	XX (XX.X%)
re-started with dose delay but no reduction	XX (XX.X%)	XX (XX.X%)	XX (XX.X%)
re-started with dose reduction but no delay	XX (XX.X%)	XX (XX.X%)	XX (XX.X%)
re-started without dose delay or reduction	XX (XX.X%)	XX (XX.X%)	XX (XX.X%)
not re-started	XX (XX.X%)	XX (XX.X%)	XX (XX.X%)
Not resolved, re-started	XX (XX.X%)	XX (XX.X%)	XX (XX.X%)

CONFIDENTIAL

205678

with dose delay and reduction	XX (XX.X%)	XX (XX.X%)	XX (XX.X%)
with dose delay but no reduction	XX (XX.X%)	XX (XX.X%)	XX (XX.X%)
with dose reduction but no delay	XX (XX.X%)	XX (XX.X%)	XX (XX.X%)
without dose delay or reduction	XX (XX.X%)	XX (XX.X%)	XX (XX.X%)
Not resolved, not re-started	XX (XX.X%)	XX (XX.X%)	XX (XX.X%)
not discontinued	XX (XX.X%)	XX (XX.X%)	XX (XX.X%)
discontinued, follow up ongoing	XX (XX.X%)	XX (XX.X%)	XX (XX.X%)
discontinued, follow up ended	XX (XX.X%)	XX (XX.X%)	XX (XX.X%)
Duration of first occurrence [1] [2]			
n	XX	XX	XX
Mean	XX.X	XX.X	XX.X
SD	XX.XX	XX.XX	XX.XX
Median	XX.X	XX.X	XX.X
Min.	XX	XX	XX
Max.	XX	XX	XX
Number of occurrences (based on subjects with the event)			
One	XX (XX.X%)	XX (XX.X%)	XX (XX.X%)
Two	XX (XX.X%)	XX (XX.X%)	XX (XX.X%)
Three or more	XX (XX.X%)	XX (XX.X%)	XX (XX.X%)
Outcome post treatment exposure			
Number of of subjects with unresolved Event at the end of treatment exposure, or with event onset post treatment exposure.	xx	xx	xx
Resolved	XX (XX.X%)	XX (XX.X%)	XX (XX.X%)
Not resolved, follow up ongoing	XX (XX.X%)	XX (XX.X%)	XX (XX.X%)

Not resolved, follow up ended	XX (XX.X%)	XX (XX.X%)	XX (XX.X%)
Time to resolution post treatment exposure, days			
n	XX	XX	XX
Mean	XX.X	XX.X	XX.X
SD	XX.XX	XX.XX	XX.XX
Median	XX.X	XX.X	XX.X
Min.	XX	XX	XX
Max.	XX	XX	XX

[1] The duration is defined as time from onset of any **blurred vision** event to the first time the subject is free of any such event. It requires at least one day gap between the resolution of all events from first occurrence to the onset of second occurrence.

[2] Imputed AE stop date was used in the calculation of duration if the outcome of the event was resolved/resolved with sequelae and AE stop date was partial with day missing. Imputed AE start date was used in the calculation if the start date was partial with day missing.

[3] The end of treatment exposure is defined as last infusion date +20 days.

Programming note:

a. The event term (e.g. blurred vision) in footnote 1 need to be updated to be consistent with the title. b. Time to resolution post treatment exposure is calculated as (AE end date – end of treatment exposure) if there is unresolved event at the end of treatment exposure, or (first time the subject is free of any such event – onset date) if there is no unresolved event at the end of treatment exposure but with event onset post treatment exposure.

Example SAFE_T22
 Protocol: 205678
 Population: Full Safety

Table x.xxxx

Summary of Percentage of Duration of Exposure with Blurred Vision (CTCAE)

	2.5 mg/kg (N=97)	3.4 mg/kg (N=96)	3.4 mg/kg Lyo (N=25)

Percentage of Duration of Exposure			
n	48	31	11
Mean	52.9	46.8	42.8
SD	24.31	28.00	24.27
Median	55.4	51.2	48.8
Min.	2	2	5
Max.	95	89	75
Category of Percentage of Duration of Exposure			
n	48	31	11
>0 to <=20%	6 (13%)	8 (26%)	3 (27%)
> 20% to <= 40%	8 (17%)	6 (19%)	1 (9%)
> 40% to <= 60%	13 (27%)	4 (13%)	3 (27%)
> 60% to <= 80%	13 (27%)	9 (29%)	4 (36%)
> 80% to <= 100%	8 (17%)	4 (13%)	0

Note: n denotes the number of subjects with corneal events (CTCAE) of maximum grade ≥ 2 during exposure of study treatment.

Example: PRO_T1
 Protocol: 205678
 Population: ITT

Page 1 of 1
 (Data as of: 30MAY2001)

Table x.xxxx

Summary of Change in EORTC QLQ-C30/EORTC QLQ-MY20 Summary Score/Domain Scores from Baseline by Visit

summary score/domain score names (Physical Functioning, Role Functioning, etc)

Timepoint			Treatment Group A (N=xxx)	Treatment Group B (N=xxx)
Baseline	Actual Score	n	xxx	xxx
		Mean	x.x	x.x
		SD	x.xx	x.xx
		Median	x.x	x.x
		Min	x	X
		Max	xxx	xxx
Week 4	Actual Score	n	xxx	xxx
		Mean	x.x	x.x
		SD	x.xx	x.xx
		Median	x.x	x.x
		Min	x	x
		Max	xxx	xxx
	Change from Baseline	n	xxx	xxx
		Mean	x.x	x.x
		SD	x.xx	x.xx
		Median	x.x	x.x
		Min	x	x
		Max	xxx	xxx
Week x	Actual Score	n	xxx	xxx
		Mean	x.x	x.x
		SD	x.xx	x.xx
		Median	x.x	x.x
		Min	x	x
		Max	xxx	xxx
	Change from Baseline	n	xxx	xxx
		Mean	x.x	x.x
		SD	x.xx	x.xx
		Median	x.x	x.x
		Min	x	x
		Max	xxx	xxx

Example: PRO_T2
Protocol: 205678
Population: ITT

Page 1 of 1
(Data as of: 30MAY2001)

Table x.xxxx

Number (%) of patient with improvement in EORTC QLQ-C30EORTC QLQ-MY20 summary score/domain scores \geq 5/10/MID by visit

summary score/domain score names (Physical Functioning, Role Functioning, etc)

Timepoint		Treatment	Treatment
		Group A	Group B
		(N=xxx)	(N=xxx)
Week 4	N	xxx	xxx
	summary score/domain scores \geq 5/10/MID	xxx (xx%)	xxx (xx%)
Week x	n	xxx	xxx
	summary score/domain scores \geq 5/10/MID	xxx (xx%)	xxx (xx%)

Example: PRO_T3
 Protocol: 205678
 Population: Safety

Page 1 of 1
 (Data as of: 30MAY2001)

Table x.xxxx

Summary of maximum post-baseline PRO-CTCAE score

	Treatment Group A (N=xxx)			Treatment Group B (N=xxx)		
	Frequency	Severity	Interference	Frequency	Severity	Interference
Item x	n=xxx	n=xxx	n=xxx	n=xxx	n=xxx	n=xxx
Response						
0	xx (xx%)	xx (xx%)	xx (xx%)	xx (xx%)	xx (xx%)	xx (xx%)
1	xx (xx%)	xx (xx%)	xx (xx%)	xx (xx%)	xx (xx%)	xx (xx%)
2	xx (xx%)	xx (xx%)	xx (xx%)	xx (xx%)	xx (xx%)	xx (xx%)
3	xx (xx%)	xx (xx%)	xx (xx%)	xx (xx%)	xx (xx%)	xx (xx%)
4	xx (xx%)	xx (xx%)	xx (xx%)	xx (xx%)	xx (xx%)	xx (xx%)
3+4	xx (xx%)	xx (xx%)	xx (xx%)	xx (xx%)	xx (xx%)	xx (xx%)
Any Scale >0	xx (xx%)	xx (xx%)	xx (xx%)	xx (xx%)	xx (xx%)	xx (xx%)
Item y	n=xxx	n=xxx	n=xxx	n=xxx	n=xxx	n=xxx
Response Scale						
0	xx (xx%)	xx (xx%)	xx (xx%)	xx (xx%)	xx (xx%)	xx (xx%)
1	xx (xx%)	xx (xx%)	xx (xx%)	xx (xx%)	xx (xx%)	xx (xx%)
2	xx (xx%)	xx (xx%)	xx (xx%)	xx (xx%)	xx (xx%)	xx (xx%)
3	xx (xx%)	xx (xx%)	xx (xx%)	xx (xx%)	xx (xx%)	xx (xx%)
4	xx (xx%)	xx (xx%)	xx (xx%)	xx (xx%)	xx (xx%)	xx (xx%)
3+4	xx (xx%)	xx (xx%)	xx (xx%)	xx (xx%)	xx (xx%)	xx (xx%)
Any Scale >0	xx (xx%)	xx (xx%)	xx (xx%)	xx (xx%)	xx (xx%)	xx (xx%)

Note: For frequency levels, response scale stands for: 0-Never, 1-Rarely, 2-Occasionally, 3-Frequently, 4-Almost Constantly; for severity levels, response scale stands for: 0-None, 1-Mild, 2-Moderate, 3-Severe, 4-Very severe; for interference levels, response scale stands for: 0-Not at all, 1-A little bit, 2-Somewhat, 3-Quite a bit, 4-Very much.

Note: n1-n3 are the number of participants with at least one post-baseline response scale of the three attributes for a given item, which are used as denominator for calculation of percentage.

Example: PRO_T4
 Protocol: 205678
 Population: ITT

Page 1 of 1
 (Data as of: 30MAY2001)

Table x.xxxx

Summary of Worst Change from Baseline in NEI-VFQ-25 Overall Composite Score by Worst Grade of Corneal Event (GSK Scale)

		Frozen Liquid (2.5 + 3.4 mg/kg) + Lyo (3.4 mg/kg)			
		Worst Grade = 0	Worst Grade = 1,2	Worst Grade = 3,4	
		(N=xxx)	(N=xxx)	(N=xxx)	
Baseline	Actual Score	n	xx	xx	xx
		Mean	x.x	x.x	x.x
		SD	x.xx	x.xx	x.xx
		Median	x.x	x.x	x.x
		Min	x.x	x.x	x.x
		Max	xx.x	xx.x	xx.x
Worst Post-baseline	Actual Score	n	xx	xx	xx
		Mean	x.x	x.x	x.x
		SD	x.xx	x.xx	x.xx
		Median	x.x	x.x	x.x
		Min	x.x	x.x	x.x
		Max	xx.x	xx.x	xx.x
	Change from Baseline	n	xx	xx	xx
		Mean	x.x	x.x	x.x
		SD	x.xx	x.xx	x.xx
		Median	x.x	x.x	x.x
		Min	x.x	x.x	x.x
		Max	xx.x	xx.x	xx.x

[figure not shown]
Example: PRO_F1
Protocol: 205678
Population: Safety

Page 1 of 1
(Data as of: 30MAY2001)

Figure x.xxxx

Stacked Bar Chart of PRO-CTCAE Score by Attributes and Visit

Item X

Programming note: There is flexibility in choosing colour.

Example SAFE_L2
 Protocol: 205678
 Population: Safety

Page 1 of 1
 (Data as of: 24APR2018)

Listing X
 Listing of Corneal Findings (GSK Scale)

Treatment Group A

Centre Id/ Subj.	Age (y) / Sex/ Race	Eye	Grade/ Exam Finding(s)	Overall Grade of Corneal Examination Findings/Visual Acuity Grade/Overall Grade for GSK Scale for this eye	Date of Assessment /Visit	Time Since 1st Dose/ Last Dose	Action(s) Taken with study treatment/ Related
PPD [redacted]	PPD [redacted]	Left	Grade 2/ Moderate keratopathy, Grade 3/Diffuse Epithelial or stromal edema	Grade 3/ Not Applicable/ Grade 3	PPD [redacted] / Week 4	15 d/ 10 d	Dose reduced, Dose interrupted/delaye d/ No
		Right	Grade 3/ Diffuse microcysts	Grade 3/ Grade 1/ Grade 3	PPD [redacted] / Week 4	30 d/ 0 d	Dose interrupted/delaye d/ Yes
		Left	Grade 1/Mild superficial keratopathy	Grade 1/ Not Applicable/ Grade 1	PPD [redacted] / Week 7	32 d/ 0 d	Dose interrupted/delaye d / No
		Right	Grade 1/Mild superficial keratopathy	Grade 1/ Not Applicable/ Grade 1	PPD [redacted] / Week 7	32 d/ 0 d	Dose interrupted/delaye d /No

Treatment Group B

 Treatment Group C

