8.2.3. Corneal events (GSK scale)

Following discussions with regulatory agencies, GSK developed a grading scale to capture both corneal examination findings and visual acuity changes in participants treated with GSK2857916. This GSK scale differs from the CTCAE criteria for eye disorders which relies mainly on patient's symptoms and patient's ability to attend to 'activities of daily living' for grading of events. Details of derivation this GSK scale based on corneal findings and visual acuity Ophthalmic Exam (collected from Ocular

form) can be found in Appendix 9 Table 22 and Table 23 of study protocol (Version: GSK Document Number [TMF-13990464](#)).

In addition to the listing, the following outputs will be provided for corneal events graded using the GSK scale:

1. Overview for corneal event (GSK scale)
2. Summary of grade of GSK scale
 - a. Summary of characteristics of corneal events (GSK scale) including the percentage of duration of exposure (see Section 15.6.2 for definition) with corneal events (GSK scale) of grade ≥ 2 and grade ≥ 3 respectively
 - b. Summary of onset time and duration of the first occurrence of corneal event (GSK scale) of a) grade 2 or above; 2) grade 3 or above.
3. Summary of actions taken with study treatment (e.g. dose reduction/delay/permanent discontinuation)
4. Summary of time to re-initiation of study treatment post treatment delay due to corneal events (GSK scale)
5. Change in grade of corneal events (GSK scale) from EOT to last follow-up
6. Summary of worst post-baseline corneal events (GSK scale)
7. Summary of worst post-baseline corneal events (GSK scale) by best response (PR or better vs. otherwise)
8. Summary of resolution (improve to grade 1 or better) in corneal events (GSK scale) during Follow-up period (from EOT visit to last follow-up visit).
9. Logistic regression analysis will be performed to explore possible risk factors for developing corneal Events (GSK scale ≥ 2). In addition to dose arm (3.4 mg/kg vs 2.5 mg/kg), Sex (Male vs Female), Age Group (< 65 vs. ≥ 65 years), Race (White, Other), the following risk factors will also be considered:
 - a. History of intraocular surgery: (Yes vs. No)
 - b. Lens status (pseudophakia vs natural lens) at baseline
 - c. Known history of dry eye per screening questionnaire (Presence vs. Absence)
 - d. Presence of keratopathy at baseline exam (None vs. Mild vs. Moderate/Severe)

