2. General study from EOT visit to last follow-up visit: To assess the change in corneal findings after discontinuation of study treatment, among eyes and subjects (worse eye) with exam finding at EOT visit worse than baseline, the following analyses will be performed.
- a. Summary of change (worsening, no change, improvement) from EOT to last follow-up visit based on categories defined below by eye (R/L) and subject (worse eye)
 - b. Summary of number (%) of eyes and subjects (worse eye) that resolve (improve to baseline level or better based on categories defined below), and descriptive summary of time from EOT visit to resolution among eyes and subjects (worse eye) that resolved

The parameters included in above analyses are:

1. BCVA change from baseline in log MAR scale (< 0.12 , ≥ 0.12 to < 0.3 , ≥ 0.3)
 2. IOP (≥ 22 mm Hg/ <22 mm Hg)
 3. Corneal epithelium (Normal/Abnormal), Punctate Keratopathy (None/Mild /Moderate/Severe), Corneal ulcer (No/Yes), Microcystic edema (No/Yes), Microcystic without edema (No/Yes), Subepithelial haze (No to Yes), Corneal neovascularization (No to Yes), Stroma (Normal/Abnormal); Active opacity (No/Yes); Active edema (No/Yes)
 4. Corneal endothelium (Normal/Abnormal), Descemet's folds (No/Yes; Peripheral/Central), Endothelial lesion (Peripheral/Central)
 5. Pachymetry (increase from baseline $< 5\%$, and $\geq 5\%$), Tear break up time (≤ 5 mm, > 5 and ≤ 10 mm, and > 10 mm), Schirmer's test (≤ 5 sec, > 5 and ≤ 10 sec, and > 10 sec)
3. Ocular sub-study (Cycle 1-4): To evaluate the effect of topical corticosteroids on corneal findings, pending on the availability of data, the following analyses will be performed in up to 30 participants who will receive monocular topical corticosteroids for the first 4 cycles:
- a. Summary of worst grade during Cycle 1-4 of corneal events (GSK scale) in eyes randomized to topical corticosteroids treatment and eyes not.
 - b. BCVA at baseline, at worst during Cycle 1-4, and worst and most frequent category (definite worsen, possible worsen, and no change/improved) of change from baseline during Cycle 1-4 will be summarized in eyes randomized to topical corticosteroids treatment and eyes not. Eyes with a decline in BCVA to 'light perception' (LP) or 'no light perception' (NLP) due to corneal finding anytime post-baseline will also be summarized.

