Table X
 Summary of Resolution Time from EOT in Best Corrected Visual Acuity (BCVA)

Parameter = Best Corrected Visual Acuity (BCVA)

	Treatment	Treatment
Right eye: n [1]	100	100
Number (%) of eyes that resolved [2]	50 (50%)	40 (40%)
Time from EOT Visit to resolution, days		
Mean	20.5	15.1
SD	1.44	1.24
Median	18	14
Min.	3	1
Max.	40	30
Left eye: n [1]	100	100
Number (%) of eyes that resolved [2]	50 (50%)	40 (40%)
Time from EOT Visit to resolution, days		
Mean	20.5	15.1
SD	1.44	1.24
Median	18	14
Min.	3	1
Max.	40	30
Subject (worse eye): n [1]	100	100
Number (%) of subjects that resolved [2]	50 (50%)	40 (40%)
Time from EOT Visit to resolution, days		
Mean	20.5	15.1
SD	1.44	1.24
Median	18	14
Min.	3	1
Max.	40	30

Note:

1: n is the number of eyes or subjects (worse eye) with exam result worse than baseline at EOT, which will be used as denominator to calculate the percentage.

2: Resolution is defined as improvement to baseline level or better.

Example SAFE_T4a

Protocol: 205678
 Population: Safety

Page 1 of 1
 (Data as of: 24APR2018)

Table X
 Summary of Resolution in Corneal Events (GSK Scale) during Follow-up Period

	Treatment Group A (N=100)	Treatment Group B (N=100)
n [1]	100	100
Number (%) of Participants that Resolve[2]	50 (50%)	40 (40%)
Time from EOT Visit to resolution[3], days		
Mean	20.5	15.1
SD	1.44	1.24
Median	18	14
Min.	3	1
Max.	40	30

Note:

- 1: n reflects the number of participants who had corneal event (GSK Scale) with grade worse than baseline at EOT
- 2: Resolution is defined as improvement to grade 1 or better
- 3: Calculated as the date of resolution minus the (last dose date +20 days).

Example SAFE_T4b
 Protocol: 205678
 Population: Safety

Page 1 of 1
 (Data as of: 24APR2018)

Table X

Summary of Time to Re-initiation of Study Treatment Post First Treatment Delay due to Corneal Events (GSK scale)

	Treatment Group A (N=100)	Treatment Group B (N=100)
Number (%) of subjects with treatment delay due to corneal event (GSK scale)	43	33
Re-initiation of study treatment	22 (51%)	19 (58%)
Time to re-initiation [1], days		
Mean	20.5	15.1
SD	1.44	1.24
Median	18	14
Min.	3	1
Max.	40	30

Note:

1: Time to re-initiation of study treatment is calculated as the date of first dose post treatment delay minus (the date of last dose prior to treatment delay +21).

Example SAFE_T5

Protocol: 205678
 Population: Safety

Page 1 of 1
 (Data as of: 24APR2018)

Table x.xxxx

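### SAFE_T4a (Table 3.0420) selects participants by worsening from baseline but judges resolution by a fixed grade, and its time row is calculated from a different date than its label states

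*SAP*

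**What the plan says.** All of this is in the SAP. Table 3.0420 is listed in Section 15.13.8 for SAC [1] and SAC [2] and uses shell SAFE_T4a in Appendix 14 (Section 15.14).

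- **Who is in n** (SAFE_T4a, note 1): "n reflects the number of participants who had corneal event (GSK Scale) with grade worse than baseline at EOT".
- **What resolution means** (note 2): "Resolution is defined as improvement to grade 1 or better". Section 8.2.3, item 8, uses the same threshold and sets the period as "during Follow-up period (from EOT visit to last follow-up visit".
- **Time row label**: "Time from EOT Visit to resolution[3], days".
- **How the time is calculated** (note 3): "Calculated as the date of resolution minus the (last dose date +20 days".
- **What that date is called elsewhere** (SAFE_T21, note 3): "The end of treatment exposure is defined as last infusion date +20 days".

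The neighbouring shell SAFE_T4, for individual ophthalmic findings, also takes n relative to baseline, but its resolution is relative to baseline too: "Resolution is defined as improvement to baseline level or better". Section 8.5, item 2b, describes its time as "descriptive summary of time from EOT visit to resolution among eyes and subjects (worse eye) that resolved".

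**The concern.** Two things in one shell do not fit together.

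**Percentage.** Entry to n is relative to the participant's own baseline, while exit by resolution is an absolute level. Someone with baseline grade 0 and EOT grade 1 qualifies as worse than baseline and is already at the level that defines resolution. The plan has no rule for this case.

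**Time.** The row label, the listed title of Table 3.0420 and Section 8.2.3 item 8 all start the clock at the EOT visit. Note 3 starts it 20 days after the last dose. The SAP never equates that date with the EOT visit. SAFE_T4 puts the same row label on a time that does run from the EOT visit, so one label carries two origins.

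Corneal events on the GSK scale are an adverse event of special interest (Section 8.2), and this table reports how far they recover after treatment stops. At stake is whether its percentage and its time mean what a reader will take them to mean.

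**Working it through.** The SAP has no figure of its own to reproduce: the 50 (50%) and 40 (40%) in SAFE_T4a are placeholders.

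**Step 1: which grade pairs enter n.** Grades run from 0 to 4; grade 0 is a level in SAFE_T3, SAFE_T16 and Section 13.4. Pairs with EOT grade above baseline grade:

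| Baseline | EOT grades that enter n | Pairs |
|---|---|---|
| 0 | 1, 2, 3, 4 | 4 |
| 1 | 2, 3, 4 | 3 |
| 2 | 3, 4 | 2 |
| 3 | 4 | 1 |
| Total | | 10 |

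One pair, 0-to-1, is already at grade 1 at EOT. The other 9 have EOT grade 2 or above. Three of those (2-to-3, 2-to-4, 3-to-4) have baseline grade 2 or above and can resolve only by ending better than their own baseline.

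**Step 2: effect on the percentage.** Inputs, all assumed:

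- f = share of n that went 0 to 1
- p = resolution rate among those with EOT grade 2 or above
- q = share of 0-to-1 participants who later reach grade 0, taken as 0 to 80%

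Formulas, with n as the denominator (SAFE_T4 states this; SAFE_T4a does not):

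- Further drop required: (1−f)p + fq, which differs from p by f(q−p).
- Resolved on entry: f + (1−f)p, which exceeds p by f(1−p).
- n restricted to EOT grade 2 or above: p.

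| f | p | Further drop required | Resolved on entry | n restricted |
|---|---|---|---|---|
| 10% | 50% | 45% + 10%·q = 45–53% | 10% + 45% = 55% | 50% |
| 20% | 50% | 40% + 20%·q = 40–56% | 20% + 40% = 60% | 50% |
| 20% | 30% | 24% + 20%·q = 24–40% | 20% + 24% = 44% | 30% |

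Over f = 10–40%, p = 30–70% and q = 0–80%, the gap f(q−p) runs from 0.4 × (0 − 0.7) = −28 points to 0.4 × (0.8 − 0.3) = +20 points. Its sign depends on whether q is above or below p.

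**Step 3: effect on the time.** Let the EOT visit fall d days after the last dose (assumed), and resolution t days after that visit. The label implies t. Note 3 gives d + t − 20. The difference is d − 20 days:

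| d | Note 3 minus label |
|---|---|
| 7 | −13 days |
| 20 | 0 |
| 21 | +1 day |
| 42 | +22 days |

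If d is below 20, a resolution within 20 − d days of the visit gets a negative time. The two origins agree only at d = 20.

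**The case against.** **The wording settles the 0-to-1 case.** Note 2 and item 8 both require improvement. A participant at grade 1 at EOT who stays there has not improved; one who reaches grade 0 has. This is the more natural reading, and it makes the resolved-on-entry figures the less likely ones. It does not make the percentage coherent. Two participants with baseline grade 0 who both finish at grade 1 are classed differently: unresolved if EOT was grade 1, resolved if EOT was grade 4. Adding to note 2 that improvement is relative to the EOT grade would fix that reading in place without removing the anomaly.

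**The time formula is stated.** True: note 3 is tied to the row and gives one calculation, so the rule is not undefined. What remains is a time whose label, table title and Section 8.2.3 description name a different origin from its formula.

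**Other displays cover the ground.** In large part they do. Table 3.0911 (shell SAFE_T21) covers events of grade 2 or above after treatment exposure, with resolved and unresolved counts by follow-up status and time to resolution. Table 3.90010 and Figure 3.53010 add recovery of corneal exam findings. Further unresolved rows in SAFE_T4a are therefore not needed. But none of these tells a reader how Table 3.0420 treats 0-to-1 participants or which origin its time uses.

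**The sizes are hypothetical.** This stands. The SAP gives no f, p or q, and it refers to the protocol for the visit schedule.

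**Conclusion.** Both inconsistencies are in the current text and should be corrected. The percentage in Table 3.0420 mixes a relative entry rule with an absolute resolution level and is not coherent under either reading. The reported time differs from its label by d − 20 days.

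Size and direction are not known. Under the natural reading the gap from the rate among participants with EOT grade 2 or above is f(q−p), which can take either sign.

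Two stronger conclusions might be inferred, and the SAP does not support them. One is that the table systematically overstates recovery; that follows only if 0-to-1 participants count as resolved on entry. The other is that they add zero-day times and pull the median down; that needs both the less natural reading and the label's origin. Under note 3 such a participant would get d − 20 days, not zero.

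The effect is limited to one descriptive safety table for an adverse event of special interest. The primary ORR analysis is unaffected.

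**What to change.** In SAFE_T4a:

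1. **Restrict n** to participants whose EOT grade is 2 or above and worse than baseline. Everyone in n is then above the resolution level, 9 of the 10 grade pairs remain, and the threshold in Section 8.2.3 item 8 stays as it is. Footnote that for baseline grade 2 or above, resolution means ending better than baseline.
2. **Make the label and note 3 agree.** Either calculate from the EOT visit date, as item 8 and SAFE_T4 do, or relabel the row as time from end of treatment exposure (last dose +20 days). With the second choice, the footnote should say that the origin differs from SAFE_T4.

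The cost is a shell and footnote edit on data already collected. n becomes smaller, and 0-to-1 participants, including any who return to grade 0, leave this table. Because Table 3.0420 is also a SAC [1] output, the SAC [2] version needs a footnote stating the difference, or the SAC [1] table rerun alongside it under the revised definition.
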